4.3.3 Sensitivity analysis

Not applicable

4.3.4 Supplementary analyses

Not applicable

4.3.5 Subgroup analyses

To assess the homogeneity of the treatment effect across various subgroups, analyses will be performed on the primary endpoint on the PPAS and FAS across the following subgroups:

- Age group (2 to 9 [children], 10 to 17 [adolescents], and ≥ 18 [adults])
- Sex (Male, Female)

No statistical testing will be performed for the subgroup analyses.

4.4 SECONDARY ENDPOINT(S) ANALYSIS

4.4.1 Key/Confirmatory secondary endpoint(s)

4.4.1.1 Definition of endpoint(s)

The secondary endpoint for immunogenicity is:

Antibody titers against meningococcal serogroups A, C, Y, and W measured by hSBA assessed at baseline (D0, before vaccination) and after vaccination at D30 (+14 days) for all groups.

- hSBA vaccine seroresponse
- Proportion of subjects with hSBA titer $\geq 1:4$ and $\geq 1:8$
- hSBA GMT
- hSBA titer distribution and reverse cumulative distribution curve (RCDC)
- Proportion of subjects with hSBA titer ≥ 4 -fold rise from baseline (Visit 1, D0, before vaccination) to after vaccination (Visit 2, D30 [+14 days])

4.4.1.2 Main analytical approach

Descriptive statistics will be provided on both the PPAS and FAS for the antibody titers against meningococcal serogroups contained in each lot of MenACYW conjugate vaccine and Menactra®.

RCDC figures will be provided on both the PPAS and FAS for the antibody titers against meningococcal serogroups.

In summary, descriptive analyses on A, C, Y, and W serogroups will be included in:

- hSBA vaccine seroresponse and 95% CI
- Post-vaccination hSBA GMT and 95% CI
- hSBA GMT and 95% CI at each time point
- hSBA titer distribution and RCDC
- Proportion of subjects with hSBA titer $\geq 1:4$ and $\geq 1:8$ and 95% CI at each time point
- Proportion of subjects with ≥ 4 -fold rise of hSBA titer from pre-vaccination to post-vaccination

4.4.1.3 Subgroup analyses

Additional immunogenicity subgroup analyses by age group and sex will be performed on both the PPAS and FAS.

- hSBA vaccine seroresponse and 95% CI
- hSBA GMT and 95% CI at each time point

4.4.2 Supportive secondary endpoint(s)

Not applicable

4.5 TERTIARY/EXPLORATORY ENDPOINT(S) ANALYSIS

4.5.1 Definition of endpoint(s)

Not applicable.

4.5.2 Main analytical approach

Not applicable.

4.6 MULTIPLICITY ISSUES

Overall non-inferiority of the primary objective will be declared only if all individual null hypotheses for the primary endpoint are rejected on the PPAS by main analytical approach of [Section 4.3.2](#). Therefore, there is no issue with multiplicity.

4.7 SAFETY ANALYSES

All safety analyses will be performed on the SafAS as defined in [Section 3](#), unless otherwise specified, using the following common rules:

- The analysis of the safety variables defined in [Table 2](#) of [Section 1.2](#) will be essentially descriptive, and no testing is planned. However, the 95% CI will be provided.
- Safety data in subjects who do not belong to the SafAS will be provided (in the listings of Appendix).

4.7.1 Extent of exposure

Not applicable

4.7.2 Adverse events

General common rules for adverse events

All adverse events (AEs) will be coded to a lower-level term (LLT), preferred term (PT), and associated primary system organ class (SOC) using the MedDRA version currently in effect at Sanofi at the time of database lock.

The AE tables will be sorted as indicated in [Table 5](#).

Table 5 - Sorting of AE tables

AE presentation	Sorting rules
SOC and PT	By the primary SOC and PT alphabetical order

Safety overview

The safety overview after injection with the details below will be generated:

- Within 30 days after vaccine injection
 - Immediate unsolicited AE and adverse reaction (AR)
 - Solicited reaction
 - Solicited injection site reaction
 - Solicited systemic reaction
 - Unsolicited AE and AR
 - Unsolicited non-serious AE and AR
 - Unsolicited non-serious injection site AR
 - Unsolicited non-serious systemic AE and AR
 - AE leading to study discontinuation
 - Serious adverse event (SAE)
 - Death
- During the study
 - SAE
 - Death

The safety overview will also be generated by the following subgroups:

- (Actual) Age group (2 to 9 [children], 10 to 17 [adolescents], and ≥ 18 [adults])
- Sex (Male, Female)

Solicited reactions

The following summaries of solicited reactions within 7 days after vaccine injection will be presented using the terms prelisted in case report book (CRB):

- All and Grade 3 solicited reaction, solicited injection site reaction, and solicited systemic reaction
- Solicited reaction, each solicited injection site reaction (injection site pain, injection site erythema, injection site swelling, and injection site induration), and each solicited systemic reaction (fever, headache, malaise, and myalgia)
- Solicited injection site reactions (injection site pain, injection site erythema, injection site swelling, and injection site induration) and solicited systemic reactions (fever, headache, malaise, and myalgia) by following category:
 - By time period: D0-D3, D4-D7, D8 or later
 - By maximum intensity

- By time of onset
- By number of days of occurrence during the solicited period
- By action taken

Unsolicited AEs

The summary of unsolicited AEs within 30 days after vaccine injection with the details below will be generated:

- Immediate unsolicited AE and AR (any and Grade 3)
- Unsolicited AE and AR
- Unsolicited non-serious AE and AR (any and Grade 3)
- Unsolicited non-serious injection site AR (any and Grade 3)
- Unsolicited non-serious systemic AE and AR (any and Grade 3)
- SAE

The unsolicited non-serious AEs and ARs within 30 days after injection will also summarized by maximum intensity, time of onset and duration.

The AE summaries after vaccine injection of [Table 6](#) will be generated with number (%) of participants experiencing at least one event. In the summaries, the 95% CI of proportion and number of AE/ARs will also be presented.

The all and related SAEs within 30 days after vaccine injection and during whole study will also be summarized by seriousness criterion and outcome.

Table 6 - Analyses of adverse events

Type of AE	MedDRA levels
All unsolicited AE within 30 days	Primary SOC and PT
All unsolicited AR within 30 days	Primary SOC and PT
Unsolicited non-serious AE within 30 days	Primary SOC and PT
Unsolicited non-serious AR within 30 days	Primary SOC and PT
Immediate unsolicited non-serious AE within 30 minutes after vaccine injection within 30 days	Primary SOC and PT
Grade 3 unsolicited non-serious AE within 30 days	Primary SOC and PT
Grade 3 unsolicited non-serious AR within 30 days	Primary SOC and PT
All and related AE leading to study discontinuation within 30 days	Primary SOC and PT
All and related AE leading to study discontinuation during the whole study	Primary SOC and PT
SAE	Overview ^a

Type of AE	MedDRA levels
	Primary SOC and PT
a Will include the following SAE category: all SAEs and related SAEs within 7 days after vaccine injection, within 30 days after vaccine injection, and during whole study	

Analysis of deaths

The summary of death will be presented above in safety overview.

Analysis of adverse events of special interest (AESIs)

Not applicable.

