Definition	Pain either present spontaneously or when the injection site is touched or injected limb is mobilized	Presence of a redness including the approximate point of needle entry	Swelling at or near the injection site. Swelling or edema is caused by a fluid infiltration in tissue or cavity and, depending on the space available for the fluid to disperse, swelling may be either soft (typically) or firm (less typical) to touch and thus can be best described by looking at the size of the swelling.	Hardening at or near the injection site. Hardening is caused by a slow diffusion of the product in the tissue leading to a thick or hard area to touch at or near the injection site and thus can be best described by looking at the size of the hardening.
Intensity scale ^a	Grade 1: Easily tolerated Grade 2: Sufficiently discomforting to interfere with normal behavior or activities Grade 3: Incapacitating, unable to perform usual activities	Grade 1: >0 to <25 mm Grade 2: ≥25 to <50 mm Grade 3: ≥50 mm	Grade 1: >0 to <25 mm Grade 2: ≥25 to <50 mm Grade 3: ≥50 mm	Grade 1: >0 to <25 mm Grade 2: ≥25 to <50 mm Grade 3: ≥50 mm

a For the subjective reaction of pain, subjects or subjects' parents / legally acceptable representatives will record the intensity level (Grade 1, 2, or 3) in the diary card. For the measurable reactions of redness, swelling and hardening, they will record just the size of the reaction, and the classification as Grade 1, 2, or 3 will be assigned at the time of the statistical analysis.

Table 2 - Solicited injection site reactions for Adolescents (10 to 17 years of age) or Adults (18 to 55 years of age): terminology, definitions, and intensity scales

CRB term (MedDRA LLT)	Injection site pain	Injection site erythema	Injection site swelling	Injection site induration
Diary card term	Pain	Redness	Swelling	Hardening

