Definition	Pain either present spontaneously or when the injection site is touched or injected limb is mobilized	Presence of a redness including the approximate point of needle entry	Swelling at or near the injection site. Swelling or edema is caused by a fluid infiltration in tissue or cavity and, depending on the space available for the fluid to disperse, swelling may be either soft (typically) or firm (less typical) to touch and thus can be best described by looking at the size of the swelling.	Hardening at or near the injection site. Hardening is caused by a slow diffusion of the product in the tissue leading to a thick or hard area to touch at or near the injection site and thus can be best described by looking at the size of the hardening.
Intensity scale ^a	Grade 1: A type of adverse event that is usually transient and may require only minimal treatment or therapeutic intervention. The event does not generally interfere with usual activities of daily living. Grade 2: A type of adverse event that is usually alleviated with additional therapeutic intervention. The event interferes with usual activities of daily living, causing discomfort but poses no significant or permanent risk of harm to the research participant. Grade 3: A type of adverse event that interrupts usual activities of daily living, or significantly affects clinical status, or may require intensive therapeutic intervention.	Grade 1: ≥ 25 to ≤ 50 mm Grade 2: ≥ 51 to ≤ 100 mm Grade 3: > 100 mm	Grade 1: ≥ 25 to ≤ 50 mm Grade 2: ≥ 51 to ≤ 100 mm Grade 3: > 100 mm	Grade 1: ≥ 25 to ≤ 50 mm Grade 2: ≥ 51 to ≤ 100 mm Grade 3: > 100 mm

^a For the subjective reaction of pain, subjects or subjects' parents / legally acceptable representatives will record the intensity level (Grade 1, 2, or 3) in the diary card. For the measurable reactions of redness, swelling and hardening, they will record just the size of the reaction, and the classification as Grade 1, 2, or 3 will be assigned at the time of the statistical analysis

Table 3 - Solicited systemic reactions for Children, Adolescents or Adults (2 to 55 years of age): terminology, definitions, and intensity scales

CRB term (MedDRA LLT)	Fever	Headache	Malaise	Myalgia
Diary card term	Temperature	Headache	Feeling unwell	Muscle aches and pains

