5.4.2 Data handling conventions for safety variables

5.4.2.1 *Solicited Reactions*

Daily intensity

All daily records for solicited reactions will be derived into daily intensity according to the following classification: None, Grade 1, Grade 2, Grade 3, or Missing. The category of Unknown will be considered Missing if Unknown is recorded.

For the derivation of daily intensities, the following sequential steps will be applied:

1. Solicited reactions (except Fever/Pyrexia) with an investigator presence recorded as “No” and with all daily records missing then all daily intensities will be derived as None.
2. For a temperature partially missing after decimal point, the data will be analyzed replacing “MD” (missing data) by zero. For example, a “39.MD” daily temperature will be considered as “39.0°C” at the time of analysis.
3. For non-measurable (NM) solicited reactions, daily intensities will correspond to daily records reported in the clinical database. For measurable solicited reactions the daily measurements reported in the clinical database will be converted based upon the intensity scales defined in the protocol; this assumes a reaction that is too large to measure (NM) is Grade 3. Note the intensity could be considered “None” (not reaction) in the analysis despite being considered a reaction by the investigator (e.g., swelling measurement > 0 mm but < 25 mm in adults).

Note: The maximum intensity on the ongoing period is derived from the record of the maximum intensity/measurement after the end of the solicited period following the rule described above in “Daily intensity”.

Maximum overall intensity

Maximum overall intensity is derived from the daily intensities computed as described above in “Daily intensity” and is calculated as the maximum of the daily intensities over the period considered.

Presence

Presence is derived from the maximum overall intensity on the period considered:

- None : No presence
- Grade 1, Grade 2, or Grade 3 : Presence
- Missing : Missing presence

Subjects with at least one non-missing presence for a specific endpoint will be included in the analysis. Conversely, those without a non-missing presence will not be included in the analysis of the endpoint.

Time of onset

Time of onset is derived from the daily intensities computed as described above in “Daily intensity”. It corresponds to the first day with intensity of Grade 1, Grade 2, or Grade 3.

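### Individual injection-site reaction tables and the Grade 3 injection-site line have no age split, although redness, swelling and hardening are graded on different size scales at 2–9 and 10–55 years

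*SAP*

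**What the plan says.** **Grading.** Protocol 9.2.2.3.2 has two tables for solicited injection-site reactions. In Table 1 (2 to 9 years) the size scale for erythema, swelling and induration starts at "Grade 1: >0 to <25 mm", with Grade 2 from 25 mm to below 50 mm and Grade 3 from 50 mm. In Table 2 (10 to 17 and 18 to 55 years) Grade 1 starts at 25 mm and runs to 50 mm, Grade 2 is 51 to 100 mm, and the top category is "Grade 3: > 100 mm". Under both tables the diary holds the measurement and grades are assigned at analysis: "For the measurable reactions of redness, swelling and hardening, they will record just the size of the reaction".

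**Derivation.** SAP 5.4.2.1 converts each daily measurement with the protocol scales. "Presence is derived from the maximum overall intensity on the period considered": None means absent, and Grade 1, 2 or 3 means present. Time of onset and number of days count only days at Grade 1 or above. The SAP notes that a reaction seen by the investigator can become None in the analysis ("e.g., swelling measurement > 0 mm but < 25 mm in adults").

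**Tables.** Under the solicited-reactions heading of SAP 4.7.2 the plan lists "All and Grade 3 solicited reaction, solicited injection site reaction, and solicited systemic reaction". It then lists "Solicited injection site reactions (injection site pain, injection site erythema, injection site swelling, and injection site induration") by time period, maximum intensity, time of onset, days of occurrence and action taken. Age appears only in the part on the overview: "The safety overview will also be generated by the following subgroups", namely age group and sex. Protocol 12.1.2.1 tabulates solicited reactions by type, intensity and study group plus the endpoint categories. Age is not one of the categories in Protocol 9.2.2.2.

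**The concern.** The safety objective is descriptive, so the absolute percentages and their confidence intervals are the result that readers take away. For three of the four solicited injection-site reactions, the planned all-ages percentage has no single size definition. A 15 mm redness counts as Grade 1 erythema in a 9-year-old and as no erythema in a 10-year-old. A 50 mm swelling is Grade 3 at age 9 and Grade 1 at age 10.

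The pooled rate would then change with the share of children enrolled, even if true reaction sizes were the same at every age. The maximum-intensity table does not help a reader undo this, because its Grade 1 row combines 1–24 mm in children with 25–50 mm in older subjects. The rate on either scale cannot be recovered from the planned tables.

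**Working it through.** The plan states no figure on this point, so there is none to reproduce. The check has four steps.

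**1. Apply both scales to the same size** (Protocol Tables 1 and 2, whole millimetres):

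| Size | 2–9 years | 10–55 years |
|---|---|---|
| 1–24 mm | Grade 1 | None |
| 25–49 mm | Grade 2 | Grade 1 |
| 50 mm | Grade 3 | Grade 1 |
| 51–100 mm | Grade 3 | Grade 2 |
| above 100 mm | Grade 3 | Grade 3 |

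The grades differ at all 100 sizes from 1 to 100 mm and agree only at 0 mm and above 100 mm.

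**2. Does any planned table separate the scales?** The safety overview by age has one line for any solicited injection-site reaction, and that line includes pain. It has no row for erythema, swelling or induration and no Grade 3 solicited line. The summaries that do hold those rows have no age split. The other age splits in the SAP concern disposition, baseline characteristics and immunogenicity.

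**3. Effect on the pooled rate (illustration).** The documents give no size distribution, and the public text gives no number of subjects per age stratum, so these inputs are assumed. Let c be the share of children, a the proportion with any redness and b the proportion with 25 mm or more, with a and b the same at every age. The planned pooled rate is c·a + (1 − c)·b.

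| Assumed a, b | c = 20% | c = 1/3 | c = 50% |
|---|---|---|---|
| 30%, 10% | 0.2×30 + 0.8×10 = 14.0% | 16.7% | 20.0% |
| 15%, 10% | 0.2×15 + 0.8×10 = 11.0% | 11.7% | 12.5% |

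No entry equals a or b. The size of the effect depends on how many reactions are smaller than 25 mm.

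For Grade 3, assume one size distribution at all ages: 60% none, 20% at 10 mm, 10% at 30 mm, 7% at 70 mm and 3% at 120 mm. Grade 3 is then 7 + 3 = 10% on the 2–9 scale and 3% on the 10–55 scale. The pooled figure is 0.2×10 + 0.8×3 = 4.4% with 20% children and 0.6×10 + 0.4×3 = 7.2% with 60%.

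**4. Effect on the difference between vaccine groups.** Protocol 6.5 randomizes 1:1, stratified by children, adolescents and adults, so the age mix should be close in the two groups. Suppose the split were 63 versus 57 children out of 180. With a = 30% and b = 10%, the difference shifts by (6/180) × (30 − 10) = 0.67 percentage points.

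**The case against.** The strongest reply is that nothing inferential depends on these tables. Safety is secondary and descriptive, no test is planned, and stratified randomization protects the comparison between vaccines. The pooled row also has a defined meaning: the proportion of subjects who meet the definition set for their own age. The SAP discloses that small reactions in adults become None. The overview already gives an any-grade injection-site rate by age, and because sizes are recorded in millimetres a split could be added at reporting without affecting error rates. Finally, the illustrations rest on assumed inputs.

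Most of this is correct and limits the weight of the point. The primary objective is untouched, and the second row of the illustration shows that the effect can be small. It does not restore the meaning of the absolute rates. A percentage that meets an age-specific definition still moves with the age mix, and the overview line cannot show erythema, swelling or induration separately because pain is counted in it. That the split could be added later is a reason to specify it now.

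Two narrower objections also have force. Pain is worded differently in the two tables, but both scales turn on interference with activities, and the documents give no basis for saying how much this affects the Grade 3 line. The pain wording is therefore secondary to the size cut-offs. A pooled row cut at 25 mm would also count a 15 mm redness in a child as absent although Table 1 grades it, so such a row would have to be marked as supplementary.

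**Conclusion.** The concern holds. As written, the plan reports all-ages rates of erythema, swelling and induration, and a Grade 3 injection-site line, that combine two size definitions. The fact that the scales differ at every whole millimetre from 1 to 100 comes directly from the protocol tables and needs no assumption.

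The numerical size does rest on assumptions. In the scenarios shown, the pooled any-grade rate runs from 11.0% to 12.5% or from 14.0% to 20.0% as the share of children goes from 20% to 50%, and pooled Grade 3 runs from 4.4% to 7.2% as that share goes from 20% to 60%. The effect on the difference between vaccines is small, at 0.67 points in the imbalance tried. The change should be made for the sake of the descriptive safety results. It does not threaten the primary conclusion.

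**What to change.** In SAP 4.7.2, add the individual injection-site reaction tables (any, maximum intensity, Grade 3, onset, days) and the Grade 3 injection-site line separately for 2–9 and 10–55 years, or by the three randomization strata. For any all-ages row on erythema, swelling or induration, do one of two things:

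- label it as mixing two grading scales; or
- base it on one stated cut-off of 25 mm or more, marked as supplementary. This is a boundary in both tables (start of Grade 2 at 2–9 years, start of Grade 1 at 10–55 years).

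The protocol's grading scales stay as they are. The cost is programming and more tables, since the millimetre sizes are already recorded at every age.

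The statistical cost is wider intervals. Assume 180 per group with 60 children, and rates of 30% and 10% as above. The 95% Clopper-Pearson intervals are then:

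| Row | Count | Rate | 95% CI |
|---|---|---|---|
| 2–9 years, own scale | 18/60 | 30.0% | 18.8–43.2% |
| 10–55 years, own scale | 12/120 | 10.0% | 5.3–16.8% |
| All ages, mixed scale | 30/180 | 16.7% | 11.5–22.9% |
| All ages, 25 mm or more | 18/180 | 10.0% | 6.0–15.3% |

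The mixed row is narrower than the row for children only, but the quantity it estimates has no single definition.

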Medical and scientific judgment should be exercised in deciding whether expedited reporting is appropriate in other situations, such as IMEs that may not be immediately life-threatening or result in death or hospitalization but may jeopardize the health of the subject or may require intervention to prevent one of the other outcomes listed in the definition above. These IMEs should also usually be considered serious. Examples of such events include allergic bronchospasm requiring intensive treatment in an emergency room or at home, blood dyscrasias or convulsions that do not result in inpatient hospitalization, or the development of drug dependency or drug abuse, new-onset diabetes, or autoimmune disease.

² The term “life-threatening” refers to an event in which the subject was at risk of death at the time of the event; it does not refer to an event which hypothetically might have caused death if it were more severe.

³ All medical events leading to hospitalizations will be recorded and reported as SAEs, with the exception of: hospitalization planned before inclusion into the study or outpatient treatment with no hospitalization.

⁴ “Persistent or significant disability or incapacity” means that there is a substantial disruption of a person’s ability to carry out normal life functions.

Adverse Reaction:

All noxious and unintended responses to a medicinal product related to any dose should be considered adverse reactions (AR).

(The phrase “responses to a medicinal product” means that a causal relationship between a medicinal product and an AE is at least a reasonable possibility.)

The following additional definitions are used by the Sponsor:

Immediate Event/Reaction:

Immediate events are recorded to capture medically relevant unsolicited systemic AEs (including those related to the product administered) that occur within the first 30 minutes after vaccination.

Solicited Reaction:

A solicited reaction is an “expected” adverse reaction (sign or symptom) observed and reported under the conditions (nature and onset) prelisted in the protocol and CRB (e.g., injection site pain or headache occurring between D0 and D7 post-vaccination).

By definition, solicited reactions are to be considered as being related to the product administered.

For injectable vaccines, solicited reactions can either be solicited injection site reactions or solicited systemic reactions.

Unsolicited AE/AR:

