An unsolicited AE is an observed AE that does not fulfill the conditions prelisted in the CRB in terms of diagnosis and/or onset window post-vaccination. For example, if headache between D0 and D7 is a solicited reaction (i.e., prelisted in the protocol and CRB), then a headache starting on D7 is a solicited reaction, whereas headache starting on D8 post-vaccination is an unsolicited AE. Unsolicited AEs includes both serious (SAEs) and non-serious unsolicited AEs.

Injection Site Reaction:

An injection site reaction is an AR at and around the injection site. Injection site reactions are commonly inflammatory reactions. They are considered to be related to the product administered.

Systemic AE:

Systemic AEs are all AEs that are not injection or administration site reactions. They therefore include systemic manifestations such as headache, fever, as well as localized or topical manifestations that are not associated with the vaccination or administration site (e.g., erythema that is localized but that is not occurring at the injection site).

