9.2.2.2 Safety Endpoints

The secondary endpoints for the evaluation of safety are:

- Occurrence, nature (Medical Dictionary for Regulatory Activities [MedDRA] preferred term), duration, intensity, and relationship to vaccination, of any unsolicited systemic AEs reported in the 30 minutes after vaccination.
- Occurrence, time to onset, number of days of occurrence, intensity, action taken, and whether the reaction led to early termination from the study, of solicited (prelisted in the subject's diary card and CRF) injection site reactions occurring up to 7 days after vaccination.
- Occurrence, time to onset, number of days of occurrence, intensity, action taken, and whether the reaction led to early termination from the study, of solicited (prelisted in the subject's diary card and CRF) systemic reactions occurring up to 7 days after vaccination.
- Occurrence, nature (MedDRA preferred term), time to onset, duration, intensity, action taken, relationship to vaccination (for systemic AEs only), and whether the event led to early termination from the study, of unsolicited AEs up to Visit 2 after vaccination.
- Occurrence, nature (MedDRA preferred term), time to onset, duration, seriousness criteria, relationship to vaccination, outcome, and whether the SAE led to early termination from the study, of SAEs throughout the study from Visit 1 (D0) to Visit 2 (D30 [+14 days]) after vaccination.

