5.4.4 Missing data

5.4.4.1 Safety

No replacement will be done. In all subject listings, partial and missing data will be clearly indicated as missing.

Immediate

For unsolicited non-serious systemic AEs, a missing response to the “Immediate” field is assumed to have occurred after the 30-minute surveillance period and will not be imputed.

For SAEs, missing or partially missing elapsed time from last vaccination recorded if within 24 hours will be assumed to have occurred after the 30-minute surveillance period and will not be imputed. Such SAEs will not be considered as immediate.

Causality

Missing causality (relationship) for unsolicited non-serious AEs and SAEs will be considered at the time of analysis as related to vaccination.

Measurements

Partially missing temperatures will be handled as described in “Daily intensity” of [Section 5.4.2.1](#).

Intensity

For solicited reactions, missing intensities will be handled as described in “Daily intensity” of [Section 5.4.2.1](#). For unsolicited non-serious AEs, missing intensities will remain missing and will not be imputed.

Start Date and Stop Date

Missing or partially missing start dates for unsolicited AEs will remain missing and not be imputed. If the start date is missing or partially missing, the time of onset will be considered to be missing. Nevertheless, unsolicited AEs with missing time of onset will be included in analyses according to the visit collected.

Missing or partially missing stop dates for AEs (solicited reactions and unsolicited AEs) will remain missing and not be imputed.

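### SAP Table 6 limits its only preferred-term row for immediate events to non-serious AEs, although the endpoint covers any unsolicited systemic AE within 30 minutes

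*SAP*

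**What the plan says.** **Endpoint.** Protocol 9.2.2.2, repeated in SAP Table 2, asks for occurrence, nature as MedDRA preferred term, duration, intensity and relationship "of any unsolicited systemic AEs reported in the 30 minutes after vaccination". It sets no limit on seriousness.

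**Definitions.** Protocol 9.2.2.1 states: "Unsolicited AEs includes both serious (SAEs) and non-serious unsolicited AEs". It defines the immediate category in the same open way: "Immediate events are recorded to capture medically relevant unsolicited systemic AEs" in the first 30 minutes.

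**Counts.** In SAP 4.7.2 the safety overview has a line for immediate unsolicited AEs and ARs. The unsolicited AE summary has a line that begins "Immediate unsolicited AE and AR (any and Grade 3". Neither says non-serious, although several neighbouring lines in the same lists do.

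**Tables by term.** SAP Table 6 has one row for immediate events by primary SOC and PT: "Immediate unsolicited non-serious AE within 30 minutes after vaccine injection within 30 days".

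**Missing-data rule.** SAP 5.4.4.1 treats an SAE with missing elapsed time as having started after the 30-minute period: "Such SAEs will not be considered as immediate".

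**The concern.** The endpoint asks for the term of every immediate unsolicited systemic AE, serious or not. The one table that gives terms for the 30-minute window leaves out serious events. If a serious event occurred in that window, two things would follow. No listed table would show its term as an immediate event. The number of subjects with an immediate AE in the overview would also be larger than the number in the immediate table, with nothing in the output to explain the gap.

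The protocol gives reason to want this output to be complete. Section 1.3.2 mentions a rare and possibly severe allergic reaction. Section 6.1.1.2 requires 30 minutes of observation with emergency medication on site. Section 1.2.2.2 itself reports, for MET43, whether there were any immediate SAEs.

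**Working it through.** The plan gives no figure to reproduce on this point. The main check sets the listed outputs against the endpoint, and a short calculation then gives the likely size.

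**1. Can an SAE be immediate under the plan?** Yes. SAEs are unsolicited AEs by definition, and the definition of an immediate event does not exclude them. The rule in SAP 5.4.4.1 that keeps SAEs with missing elapsed time out of the immediate category has a purpose only if other SAEs can be in it.

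**2. Where would a serious immediate systemic AE appear?**

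| Output in SAP 4.7.2 | Includes SAEs | Identifies the event as immediate | Gives the term |
|---|---|---|---|
| Safety overview, immediate line | yes | yes | no SOC/PT level stated |
| Unsolicited AE summary, immediate line | yes | yes | no SOC/PT level stated |
| Table 6, immediate row | no | yes | yes |
| Table 6, "All unsolicited AE within 30 days" | yes | no | yes |
| Table 6, SAE row | yes | no | yes |

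The footnote to the SAE row names the periods as "all SAEs and related SAEs within 7 days after vaccine injection, within 30 days after vaccine injection, and during whole study". SAP 5.4.2.3 names only 30 days and the whole study. No SAE output is defined on 30 minutes. The further summaries by maximum intensity, time of onset and duration are also limited to non-serious events. No listed output has a yes in all three columns.

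**3. How likely is such an event?** Inputs from Protocol 1.2.2.2 (MET43):
- Subjects in the immediate-AE denominators: 2676 (MenACYW, pooled) and 635 (Menactra), so 2676 + 635 = 3311.
- Immediate SAEs reported: none.

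The exact two-sided 95% upper limit for 0 of n is 1 − 0.025^(1/n). With n = 3311, 1 − 0.025^(1/3311) = 0.00111, about 0.11%.

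Expected events among 360 subjects at that upper limit: 360 × 0.00111 = 0.40. The point estimate is zero.

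**4. A different rate that should not be used here.** MET43 also gives rates for all immediate unsolicited AEs: 10/2676 (0.4%) and 3/635 (0.5%). Applied to 360 subjects they give 360 × 0.4% = 1.4 and 360 × 0.5% = 1.8. As MET43 had no immediate SAEs, all 13 of these subjects had non-serious events, which the Table 6 row keeps.

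**The case against.** The strongest reply is that the SAP keeps serious and non-serious events in parallel streams. The Grade 3 rows of Table 6 are also non-serious only, SAEs have their own row, and SAP 5.4.4.1 identifies immediate events by a field for non-serious AEs and by elapsed time for SAEs. A row titled as non-serious is correct under its title. Protocol 12.1.2.1 also says that unsolicited AEs will be tabulated by the other categories in the endpoints. The table shells and listings are not among the documents, so such a table may exist.

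Part of this stands. The separation may be deliberate, and what is missing is one cross-classification: term by 30-minute window for SAEs. It does not remove the point. The endpoint sets no limit on seriousness, the SAP's own overview follows the endpoint, and the SAP lists no table that meets the commitment in Protocol 12.1.2.1.

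A reader might infer two stronger things, and the documents support neither.
- **That a serious immediate reaction would vanish from the report.** It would not. One case in an arm of 180 would read 0/180 only in the table titled as non-serious. It would remain 1/180 (0.56%) for its term in the all-unsolicited-AE and SAE tables, and it would be counted as immediate in the overview. With so few events, a careful reader could probably connect the two.
- **That one or two such events should be expected.** That range comes from the MET43 rate for all immediate AEs. The same paragraph reports no immediate SAEs.

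The added 30-day wording in the row label is not necessarily a slip. The overview lists immediate events under a 30-day heading, so it may be a period label.

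**Conclusion.** The mismatch is real and small. As listed, SAP Table 6 does not deliver the nature of a serious immediate event as the first safety endpoint asks, and the overview and the immediate table would disagree if one occurred. Detection and reporting of the event are not at risk, and the primary objective is unaffected. It is a minor alignment point.

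The likelihood is low: no immediate SAEs among 3311 subjects in MET43, an upper limit of about 0.11%, and at most about 0.4 expected events in 360. This rests on two assumptions: that the MET43 rate carries over from adolescents and adults aged 10 to 55 in the USA to subjects aged 2 to 55 in Japan, and that both vaccine groups can be pooled for this purpose. The mismatch itself rests only on the text, and on the assumption that the outputs not shown add no further table for this window.

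**What to change.** In SAP Table 6, change the immediate row to: *Immediate unsolicited systemic AE (serious and non-serious), within 30 minutes of vaccine injection*, by primary SOC and PT. Either remove the added 30-day wording from the label or say what it means.

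The cost is one table row and one filter in the program. No new data are needed: Protocol 9.2.2.3.3 already collects elapsed time for each SAE, and SAP 5.4.4.1 already says how to treat it when it is missing. The immediate table and the overview would then count the same events.
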